Categorical variables will be presented as frequency counts and percentages. A row or column denoted 'missing' will be included in count tabulations where necessary to account for dropouts and missing values. Percentages will be rounded to 1 decimal place and the percent will be suppressed when the count is zero. The denominator will be the number of patients in that dose schedule within the analysis set of interest unless otherwise noted.

Time-to-event variables will be analyzed using the Kaplan-Meier (KM) method. The KM estimates for quartiles and the confidence interval (CI) for the median will be presented as described below. Kaplan-Meier curves will also be plotted.

Time-to-event variables will be also analyzed by a Cox proportional hazards model.

Data listings will be created to support each table and to present all data. Data listings will be presented by treatment arm and patient number.

Although this is an open label trial, grouped evaluation of randomized treatment arms will be performed only for the pre-planned interim efficacy analyses and DSMB safety reviews as described in Section 8.0 of this document and in the DSMB charter. In order to protect the integrity of the trial and the robustness of the results, project team members, both Polyphor Ltd. and CRO personnel, will not evaluate, formally or informally, data grouped by randomized treatment arm as data are accruing over time. Procedures relating to the execution of pre-planned interim efficacy analyses and DSMB safety reviews are described in the DSMB Charter.

Important study variables to be used in the analysis, defined as follows:

- Age: Recorded as "Age" in the eCRF instead of the Date of Birth.
- Baseline:
 - For *efficacy evaluations*, the last available assessment before or at date of randomization is taken as "baseline" value or "baseline" assessment. For PRO endpoints, baseline is the mean of the PROs taken at screening and at last visit before first treatment administration with no imputation done if any of them is missing.
 - For *safety evaluations* (such as laboratory and vital signs), the last available assessment before first study treatment administration is taken as "baseline" value or "baseline" assessment. For patients who have not received any study treatment, the baseline will be the last assessment performed before randomization.
 - If patients have no value as defined above, the baseline result will be missing.

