8.5.1. EORTC-QLQ-C30 QoL

The European Organization for Research and Treatment of Cancer (EORTC) QLQ-C30 (version 3.0) is a validated instrument to measure quality of life and assess symptoms and side effects of treatment and their impact on everyday life. Analysis of the EORTC-QLQ-C30 QoL data will be performed in the PRO (3rd line+) set.

The instrument is composed of 5 multi-item functional scales (physical, role, social, emotional and cognitive functioning), a global health status/QoL scale, 3 symptom scales (fatigue, nausea/vomiting and pain), and 6 single items (financial difficulties, appetite loss, diarrhea, constipation, insomnia and dyspnea). Most items are scaled 1 to 4 except the items contributing to the global health status/QoL, which are 7-point questions. Raw scores will be transformed using a linear transformation to standardize the results so that scores range from 0 to 100.

The calculation for scoring these scales is the same in all cases:

- 1. Calculate the average of the items that contribute to the scale; this is the raw score.
- 2. Use a linear transformation to standardize the raw score, so that scores range from 0 to 100; a higher score represents a higher (i.e. better) level of functioning, or a higher (i.e. worse) level of symptoms.

Calculations for raw score and linear transformation are as follows:

Let items $I_1, I_2, \dots I_k$ be included in a scale, where k is number of items in the scale, then:

$$Raw \ Score = RS = \frac{\sum_{j=1}^{k} I_j}{k}$$

To obtain the score for functional scales: $\left\{ \mathbf{I} = -\frac{RS-1}{range} \right\} \times 100$

To obtain the score for symptom scales/items and global health status/QoL: $= \left\{\frac{RS-1}{range}\right\} \times 100$

Range is the difference between the maximum possible value of *RS* and the minimum possible value.

The structure of the EORTC-QLQ-C30 questionnaire is presented in Scoring for QLQ-C30 version 3.0

Table 4 in Appendix 14.3).

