At each assessment point, summary statistics of absolute scores and changes from baseline will be calculated by treatment arm for each scale for both the raw score and the linear transformed score. The baseline result will be the mean of the screening visit score and the score at last assessment prior to dosing. Summary tables and boxplots of the score by visit and treatment arm will be presented. The best and worst changes from baseline and associated time points will also be summarized using descriptive statistics. For functional scales and global health status, best changes from baseline are positive changes; while for symptom scales/items, best changes are negative changes.

The percentage of patients missing the entire questionnaire will be summarized and reason it is missing will be listed by treatment arm.

If more than 50% of questions are unanswered within a subscale at a particular timepoint, the value for the subscale will be set to missing. If less than 50% of questions are unanswered, the

sum of the scores for the answered questions will be taken and scaled up in relation to the number of questions in the scale answered or not.

The change from baseline for the linear transformed score will be compared between treatment arms for the PRO (3rd line+) set using mixed model repeated measures (MMRM) analysis with fixed effect terms for treatment arm, visit, treatment arm by visit interaction, the randomization stratification factors and also with baseline score as a covariate. Patient will be included as a random effect. The default estimation method of Restricted Maximum Likelihood (REML) and the Kenward-Roger (KR) option for degrees of freedom will be used. An unstructured covariance matrix will be used to model the within-patient error. If the fit of the unstructured covariance structure fails to converge, the following covariance structures will be tried in order until convergence is reached: Toeplitz with heterogeneity, autoregressive with heterogeneity, toeplitz, and autoregressive. A summary table will present number of subjects in each treatment group at each visit, LSMeans by treatment arm by visit, along with the difference in LSMeans, standard error, 95% CI and 2-sided p-value.

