Patients will also be classified as improved, stable, or worsened. Minimal important difference (MID) thresholds, a threshold of 5 score points of the linear transformed score, will be used to categorize patients as improved, stable, or worsened. The first post-baseline assessment where either improved or worsened status is met will be used to assign patient status. The improved or worsened status has to be confirmed by the assessment at subsequent cycle.

The proportion of patients with each status will be calculated for each subscale based on patients who have at least two available change from baseline of the linear transformation scores in that scale. A proportional odds model will be used to test the difference in proportions of patient status between treatment arms for each scale; a fixed effect term for treatment will be included and the model will be stratified for randomization stratification factors. The odds ratio, 95% CI and 2-sided p-value will be extracted from the model and presented.

The individual questions and derived scales scores will be listed for the PRO (3rd line+) set.

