14.3. Scoring for QLQ-C30 version 3.0

Table 4 - Scoring for QLQ-C30 version 3.0

	Scale	Number of items	Item range*	Version 3.0 Item numbers	Function scales
Global health status / OoL					
Global health status/QoL (revised) [†]	QL2	2	6	29, 30	
Functional scales					
Physical functioning (revised) [†]	PF2	5	3	1 to 5	F
Role functioning (revised) [†]	RF2	2	3	6, 7	F
Emotional functioning	EF	4	3	21 to 24	F
Cognitive functioning	CF	2	3	20, 25	F
Social functioning	SF	2	3	26, 27	F
Symptom scales / items					
Fatigue	FA	3	3	10, 12, 18	
Nausea and vomiting	NV	2	3	14, 15	
Pain	PA	2	3	9, 19	
Dyspnoea	DY	1	3	8	
Insomnia	SL	1	3	11	
Appetite loss	AP	1	3	13	
Constipation	CO	1	3	16	
Diarrhoea	DI	1	3	17	
Financial difficulties	FI	1	3	28	

Statistical Execution Plan, Version 1.0 Date Issued: 14MAY2021

4. Subscale Scoring for the FACT-B

Subscale	Item	Reverse?	Item response	Item Score	
PHYSICAL WELL	GP1	Yes	x	4 - x	
BEING	GP2	Yes	x	4 - x	
(PWB)	GP3	Yes	x	4 - x	
	GP4	Yes	x	4 - x	
	GP5	Yes	x	4 - x	
	GP6	Yes	x	4 - x	
-	GP7	Yes	x	4 - x	_
			Total		
			×7 Divide by number items answered		= PWB subscale score
SOCIAL/FAMILY WFLI	GS1	No	x	x	
BEING	GS2	No	x	x	
(SWB)	GS3	No	x	x	
	GS4	No	x	x	
	GS5	No	x	x	
	GS6	No	x	x	
-	GS7	No	x	x	_
			Total		
			×7 Divide by number items answered		= SWB subscale score
EMOTIONAL WELL	GE1	Yes	x	4 - x	
BEING	GE2	No	x	x	
(EWB)	GE3	Yes	x	4 - x	
	GE4	Yes	x	4 - x	
	GE5	Yes	x	4 - x	
-	GE6	Yes	x	4 - x	_
			Total ×6		
			Divide by number items answered		= EWB subscale score

Table 5 - Subscale Scoring for the FACT-B

Subscale	Item	Reverse?	Item response	Item	
BREAST	Item		item response		
CANCER	B1	Yes	x	4-x	
SUBSCALE	B2	Yes	x	4 - x	
(BC3)	В3	Yes	x	4 - x	
	B4	No	x	x	
	В5	Yes	x	4-x	
	B6	Yes	x	4 - x	
	В7	Yes	x	4 - x	
	B8	Yes	х	4 - x	
	В9	No	х	x	
	P2	Yes	х	4 - x	_
			Total		
			×10		
			Divide by number items answered		=BC subscale score
FUNCTIONAL WELL-BEING	GF1	No	x	x	
(FWB)	GF2	No	x	x	
	GF3	No	x	x	
	GF4	No	x	x	
	GF5	No	x	x	
	GF6	No	x	x	
	GF7	No	x	x	_
			Total		
			×7		
			Divide by number		
			items answered		= FWB subscale score

Polyphor Ltd POL6326-009 **Subscale Scoring for the FACT-B (cont.)**

14.5. Algorithm for the best response determination according to RECIST v1.1 guidelines, as assessed by the local Investigator's review

- a) Patients need to have two consecutive assessments of PR or CR to be a responder. PR or CR must be confirmed by 2 consecutive tumor evaluations spaced at least 4 weeks (28 days) apart.

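### A one-step difference between the two baseline QLQ-C30 forms is enough to class a patient with no change since pre-dose as improved or worsened on 12 of 15 scales

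*SAP*

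**What the plan says.** SAP Section 8.5.1 defines the QLQ-C30 baseline as an average: "The baseline result will be the mean of the screening visit score and the score at last assessment prior to dosing". Section 4 gives the same definition for all PRO endpoints. The protocol schedule (Section 11.3) supplies both forms: one at screening, and one before the first dose, on Day 1 in the combination arm and Day 2 in the eribulin arm.

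On scoring, the SAP says "Use a linear transformation to standardize the raw score, so that scores range from 0 to 100", and on items, "Most items are scaled 1 to 4 except the items contributing to the global health status/QoL, which are 7-point questions". Appendix 14.3, "Table 4 - Scoring for QLQ-C30 version 3.0", lists the number of items and the item range for each of the 15 scales.

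For the classification, the SAP says that "a threshold of 5 score points of the linear transformed score, will be used to categorize patients as improved, stable, or worsened". On timing the SAP says "The first post-baseline assessment where either improved or worsened status is met will be used to assign patient status", and on confirmation, "The improved or worsened status has to be confirmed by the assessment at subsequent cycle". A proportional odds model then compares the three categories between arms for each scale, with an odds ratio, 95% CI and p-value.

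The SAP does not relate the 5 points to the step size of the scales, and it has no rule for patients whose two baseline scores differ.

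**The concern.** A scale with few items can take only a few values, and consecutive values lie well apart. If the two baseline scores differ by one step, their mean falls midway between two attainable values, so with complete forms no later score can equal it. If half a step exceeds 5 points, every later visit meets the threshold, whatever the patient answers.

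The classification is meant to count patients with a minimally important change. For the patients affected it instead records which way the screening form differed from the pre-dose form. The odds ratios on those scales would then contain baseline noise labelled as change on treatment.

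**Working it through.** **Inputs.** Items and item range per scale come from SAP Appendix 14.3. The transformation, the averaged baseline and the 5-point threshold come from Section 8.5.1. All forms are taken as complete. The threshold is stipulated, not derived, so there is no plan figure to reproduce. As a check on the inputs, the Appendix 14.3 values give a 0 to 100 range on all 15 scales and 30 items in total.

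**Formulas.**
- Score = (mean item − 1) / range × 100. The reversal for functional scales does not alter absolute changes.
- One step (one item moves by one category) = 100 / (items × range).
- Offset of the averaged baseline after a one-step difference = half a step.

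| Scales | Items × range | One step | Half-step | Reaches 5? |
|---|---|---|---|---|
| Six single items | 1 × 3 | 33.3 | 16.7 | yes |
| Role, cognitive, social, nausea/vomiting, pain | 2 × 3 | 16.7 | 8.3 | yes |
| Fatigue | 3 × 3 | 11.1 | 5.6 | yes |
| Emotional | 4 × 3 | 8.3 | 4.2 | no |
| Global health status | 2 × 6 | 8.3 | 4.2 | no |
| Physical | 5 × 3 | 6.7 | 3.3 | no |

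Scales that reach 5: 6 + 5 + 1 = 12 of 15. No half-step equals 5, so it does not matter whether a change of exactly 5 counts.

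**Example: pain.**
1. Screening answers 3 and 2: mean 2.5, score 1.5/3 × 100 = 50.0.
2. Pre-dose answers 2 and 2: mean 2, score 1/3 × 100 = 33.3.
3. Baseline = (50.0 + 33.3)/2 = 41.7.
4. Answers 2 and 2 at every later cycle: change = 33.3 − 41.7 = −8.3, which is improved.
5. The next cycle gives −8.3 again, so the status is confirmed.

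The patient's answers have not changed since pre-dose. With the two baseline forms swapped and the later answers again equal to the pre-dose ones, the change is +8.3 and the patient is classed as worsened.

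**Variations.**
- Same answers at screening, pre-dose and every cycle: change 0, stable on 15 of 15 scales.
- Two baseline steps apart in the same direction: the offset is one full step, at least 6.7, so all 15 scales are affected.
- Equal baseline scores: the smallest non-zero later change is one step, also at least 6.7. The 5-point threshold therefore never screens out a one-step change, and stable at a visit means zero net change.

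**The case against.** **A stronger reading is not supported.** A reader might infer that patients whose answers never change at all are misclassified. They are not: identical answers throughout give a change of 0. The error needs a difference between the screening and pre-dose forms, followed by steady answers.

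**Confirmation does some work.** If later answers keep moving between the same two categories, the change alternates in sign and confirmation fails. Such a patient presumably ends as stable, although the SAP does not say so. The error is certain only when later answers hold steady. This stands, and for that reason the stable category does not disappear for everyone with differing baseline forms.

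**Size is not shown.** The 12 of 15 counts scales, not patients. The documents give no rate of screening-to-pre-dose differences. Any assumed rate would give the share exposed, not the share misclassified. This stands.

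**Both arms follow the same rule.** The plausible effect is dilution of the odds ratios, and nothing in the documents shows that baseline noise drives them. This stands too, with one qualification: the pre-dose form is completed after open-label randomization (Protocol Sections 7.3.1.1 and 7.4.1) and on different days in the two arms, so balance is not guaranteed.

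**Little depends on it.** QLQ-C30 is exploratory, without Type I error control (SAP Section 8.5). The protocol (Section 12.2.7.5) specifies a mixed model for repeated measures, which needs no threshold. This limits the importance of the point but does not make the rule right.

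**Conclusion.** The concern holds in a limited form. A one-step difference between the screening and pre-dose answers is enough to class a patient with no change since pre-dose as improved or worsened on 12 of 15 scales. The offsets are 16.7, 8.3 and 5.6 points against a threshold of 5, and confirmation does not prevent this when later answers hold steady. The result assumes complete forms and follows from the SAP's own scoring table.

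The responder odds ratios are contaminated by baseline noise to an unknown extent. A reader might go further and conclude that they are driven by it, or that a stated percentage of patients is misclassified; the documents support neither. No primary, key secondary or other secondary result is affected. This is a minor point that is cheap to correct.

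**What to change.** Change the responder classification only; the repeated-measures model can keep its averaged baseline. The threshold must exceed half a response step. Either version below achieves this for one-step baseline differences.

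1. **Keep the averaged baseline.** Require at least 10 points on multi-item scales (largest half-step 8.3) and more than 16.7 points on the six single items. A uniform 10 points would leave the single items uncorrected. Baseline differences of two steps would still produce the artefact on the 12 scales (11.1 to 33.3 points).
2. **Use one pre-dose score as baseline, with a 10-point threshold.** A patient unchanged since pre-dose is then stable on 15 of 15 scales. The baseline change alone is not enough. A patient who answers one way at screening, one step differently at pre-dose and then as at screening is 3.3 to 4.2 points from the averaged baseline on physical, emotional and global health. The same patient is 6.7 to 8.3 points from the single pre-dose score, which would count as change at 5 points. On the other 12 scales this patient would still be called changed under this version, since a full step there is at least 11.1.

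The documents justify neither 5 nor 10 points against step size, so the SAP should state the rationale for the value chosen.

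**Cost.** New wording and one derivation in SAP Section 8.5.1. Fewer patients will be called changed, mainly those with one-step shifts on physical (6.7), emotional and global health (8.3). The second version also rests the baseline wholly on a form completed after open-label randomization.

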11.3 Patient Reported Outcomes

Patient reported outcomes (PROs) of health-related QoL and health status will be assessed using the EORTC-QLQ-C30, FACT-B and EQ-5D instruments. Patients will complete each instrument at the Screening Visit and at the EoT visit. Patients on the balixafortide + eribulin treatment arm will also complete each instrument pre-dose on Day 1 of each cycle. Patients on the eribulin monotherapy treatment arm will also complete each instrument pre-dose on Day 2 of each cycle. These instruments should be completed in the same sequence at each scheduled assessment.

During the study treatment phase, patients must complete these instruments in clinic (cannot be taken home) and prior to having any clinical assessments, drug dosing, diagnostic testing, and to any discussion of their progress with healthcare personnel at the site. Interviewer administration in clinic may be used under special circumstances (e.g. patient forgot their glasses or feels too ill).

The EORTC-QLQ-C30 is a validated instrument to measure QoL and assess symptoms and side effects of treatment and their impact on everyday life. The instrument is composed of 5 multi-item functional scales (physical, role, social, emotional and cognitive functioning), a global health status/QoL scale, 3 symptom scales (fatigue, nausea/vomiting and pain), and 6 single items (financial difficulties, appetite loss, diarrhea, constipation, insomnia and dyspnea).

PROs of health-related QoL and health status will be assessed using the FACT-B and EQ-5D instruments. The FACT-B and EQ-5D will be given to the patient in the appropriate language.

The EQ-5D consists of two parts, the EQ-5D descriptive system and the EQ Visual Analogue scale (EQ VAS). The descriptive system comprises 5 dimensions: mobility, self-care, usual activities, pain/discomfort, anxiety/depression. Each dimension has 5 levels: no problems, slight problems, moderate problems, severe problems, and extreme problems. The EQ VAS records the patient's self-rated health visual analogue scale with endpoints labelled 'the best health you can imagine' and 'the worst health you can imagine'.

FACT-B is a self-administered questionnaire designed for patient suffering from BC. It consists of 5 subscales (physical wellbeing, social/family wellbeing, emotional wellbeing, functional wellbeing, breast subscale)

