The local Investigator will assess the presence of disease following CT/MRI scan performed at Screening, and those performed subsequently, and record the details in the patient's source data and eCRF relative to the previous assessment of disease status/metastatic burden.

A blinded Independent Review Committee (IRC) will perform a retrospective review of radiographic images and relevant clinical information collected on-study to assess the protocol defined endpoints of disease response and progression.

Following initial documentation of an objective response, a confirmatory CT/MRI scan will be performed at least 4 weeks later.

Patients discontinuing the study treatment for reasons other than death will attend an End of Treatment (EoT) visit as soon as possible, within 7 days after discontinuation and prior to initiation of any new anti-cancer therapy, regardless of the reason for discontinuation. A physical examination will be conducted, adverse events (AEs), Eastern Cooperative Oncology Group (ECOG) performance status, vital signs, clinical laboratory,12-lead Electrocardiogram (ECG), concomitant medications and Patient reported health outcome QoL questionnaires will be assessed and recorded for all patients at the EOT visit. Furthermore, tumor assessments should be conducted for patients who discontinued from study treatment in the absence of PD.

A 30-day safety follow-up visit will be performed within 30 days (and no later than 37 days) from the last dose of study treatment. Patients discontinuing the study treatment phase for any reason, without PD (i.e. due to unacceptable adverse events) will enter the long-term follow-up (PD follow-up and survival follow-up).

Patients who are discontinued from study treatment for any reason, in the absence of PD, will undergo repeat imaging and tumor response assessments every 8 weeks \pm 7 days (every 12 weeks \pm 7 days if the patient has been on the study for >= 1 year), regardless of regimen, until PD is documented, or death occurs, or patient is lost to follow-up, or the patient withdraws consent (whichever occurs first). If a patient stops study treatment and begins another anti-cancer therapy before PD is documented, the new anti-cancer treatment should be recorded in the patient's source data and eCRF and every effort should be made to perform tumor evaluation in these patients until disease progression.

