All patients will be followed for OS status every 6 months until death, until the patient withdraws consent to follow-up for survival or until the patient is lost to follow-up (whichever occurs first).

Patients will complete the European Organization for the Research and Treatment of Cancer Quality of Life Questionnaire Core 30 (EORTC-QLQ-C30) Quality of Life (QoL), Functional Assessment of Cancer Therapy Breast (FACT-B) and EuroQol-5D (EQ-5D) questionnaires during the screening period, prior to first dose, and at the start of each subsequent cycle of study treatment during while still in receipt of study treatment.

An independent data safety monitoring board (DSMB) will review patient safety during the trial and will provide oversight of the planned, formal interim efficacy analyses.

The enrolment period is expected to be approximately 12 months, with an expected 12 months further follow-up prior to the analysis of PFS and an additional 12 months follow-up thereafter to the final analysis of OS. The overall trial duration (from first patient randomized until the end of the trial) is therefore projected to be approximately 36 months.

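### As worded, the QLQ-C30 confirmation rule in SAP 8.5.1 does not let the End of Treatment form confirm a change, so worsening around treatment stop is probably under-counted in one exploratory analysis

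*SAP*

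**What the plan says.** SAP 8.5.1 sets a threshold of 5 points on the transformed QLQ-C30 score and sorts patients into improved, stable or worsened. Three rules follow.

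- Assignment: "The first post-baseline assessment where either improved or worsened status is met will be used to assign patient status".
- Confirmation: "The improved or worsened status has to be confirmed by the assessment at subsequent cycle".
- Denominator: proportions are "based on patients who have at least two available change from baseline of the linear transformation scores in that scale".

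The arms are then compared scale by scale: "A proportional odds model will be used to test the difference in proportions of patient status between treatment arms for each scale".

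On collection, SAP 3.1 schedules the questionnaires during screening, "prior to first dose, and at the start of each subsequent cycle of study treatment during while still in receipt of study treatment". The same section adds that "Patient reported health outcome QoL questionnaires will be assessed and recorded for all patients at the EOT visit", and Protocol 11.3 agrees: "Patients will complete each instrument at the Screening Visit and at the EoT visit". EoT falls within 7 days of discontinuation (SAP 3.1; Protocol 7.6). The schedules of assessments (Protocol Tables 1 to 3; SAP Appendix 14.1) show no questionnaire at the 30-day safety visit or in long-term follow-up.

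SAP 8.5.1 does not say whether the EoT form can act as the confirming assessment, which category an unconfirmed change receives, or how stopping for progression, toxicity or death is handled in this classification.

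**The concern.** The confirmation rule is tied to a further cycle, but a patient who stops treatment has no further cycle. The only form left is EoT, and the wording does not admit it. A worsening that appears on the last cycle form and is repeated at EoT has been observed twice, yet fails the rule as written. A worsening that first appears at EoT fails under any reading, because no form comes after it.

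EoT is where deterioration would be expected to show, since progression or toxicity has often just ended treatment. The table of improved, stable and worsened patients would then understate worsening. If time on treatment differs between arms, as the PFS assumptions imply, the understatement may also differ, and the odds ratio would carry some of that difference. There is a practical side as well: two programmers could derive different categories and different denominators from the same text.

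**Working it through.** The documents give no figure for this classification, so there is none to reproduce. The PFS inputs borrowed in steps 3 and 4 are internally consistent: with hazard ratio 0.674, one-sided alpha 0.020 and 90% power (SAP 4.1), 4 × (2.054 + 1.282)² / (ln 0.674)² gives 286 events, as stated.

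**1. Forms per patient.** Cycles last 21 days (Protocol 7). Post-baseline forms fall at about day 21 (Cycle 2), day 42 (Cycle 3) and so on while on treatment, plus one EoT form.

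**2. What each reading confirms.**

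| Pattern of worsening | Only a cycle form confirms | EoT may also confirm |
|---|---|---|
| On the last two cycle forms | confirmed | confirmed |
| On the last cycle form and again at EoT | not confirmed | confirmed |
| On the last cycle form, gone at EoT | not confirmed | not confirmed |
| First seen at EoT | not confirmed | not confirmed |

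The second row is the one that the choice of wording changes. The fourth is lost either way.

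**3. Timing illustration.** Assume that time on treatment T equals PFS and is exponential with the SAP 4.1 medians: 3.9 × 30.4375 = 118.7 days (eribulin) and 5.8 × 30.4375 = 176.5 days (combination). Suppose that a lasting worsening starts a fixed time before stopping.

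- Starting 21 days before: a 21-day window holds at most one post-baseline cycle form, never two. If EoT does not count, none of these worsenings can be confirmed. If EoT counts, all can be, except in patients who stop before day 21: about 12% (eribulin) and 8% (combination).
- Starting 7 days before: most such windows hold no cycle form, so the worsening is first seen at EoT. The share is P(T<21) + P(T≥21) × (S(7) − S(21)) / (1 − S(21)), where S(t) = 2^(−t/median).
  - Eribulin: 0.115 + 0.885 × 0.653 = about 69%.
  - Combination: 0.079 + 0.921 × 0.657 = about 68%.
  - These cannot be confirmed even if EoT counts.

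**4. The two-score denominator.** Under the same assumptions:

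| Condition | Eribulin | Combination |
|---|---|---|
| EoT scores not counted: P(T<42) = 1 − 2^(−42/median) | 21.7% (about 35 of 160) | 15.2% (about 24 of 160) |
| EoT counted, stopping at any time: P(T<21) = 1 − 2^(−21/median) | 11.5% (about 18 of 160) | 7.9% (about 13 of 160) |
| EoT counted, stopping only at 6-weekly scans | near 0% | near 0% |

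The 160 is 320 third-line-plus patients randomized 1:1. The last row is near zero because a patient stopped at the first scan (Cycle 2 Day 21) has the Cycle 2 form and the EoT form.

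**5. Why confirmation is there.** From the item counts and ranges in SAP Appendix 14.3, Table 4, a one-step change on one item moves a scale by 100 / (items × range):

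- physical functioning: 100/(5 × 3) = 6.7
- global health: 100/(2 × 6) = 8.3
- emotional functioning: 100/(4 × 3) = 8.3
- fatigue: 100/(3 × 3) = 11.1
- other two-item scales: 100/(2 × 3) = 16.7
- single items: 100/3 = 33.3

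Each exceeds the 5-point threshold, so one unconfirmed reading can be noise.

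**The case against.** The strongest reply is that requiring a confirmed change is a legitimate, conservative definition, and that step 5 shows why it is needed. Waiving confirmation for terminal worsening alone would tilt the classification: a patient with one post-baseline score could be worsened but never improved. If such patients are more common on eribulin, the comparison would shift toward the combination in an open-label trial. This stands, and it rules out a worsening-only waiver as the main rule. It does not defend leaving EoT out as a confirming form.

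The reply also disposes of four stronger readings that a reader might infer.

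- That questionnaires end with the last cycle, so roughly a fifth of eribulin patients drop out of the analysis. The EoT form is scheduled for all patients and the two-score rule carries no cycle restriction, so a Cycle 2 score plus an EoT score qualifies as written. The 21.7% and 15.2% apply only if EoT is excluded.
- That unconfirmed worsening is counted as stable. This follows by elimination from three categories; the SAP does not state it.
- That improvement escapes the problem. The rule names both directions. Deterioration is more likely to coincide with stopping, but the documents do not quantify this.
- That a quality-of-life harm or benefit would be hidden. The MMRM, by-visit summaries and best and worst changes from baseline (SAP 8.5.1) need no confirmation, and the PRO set needs only one post-baseline value (SAP 4.3.8). The EQ-5D and FACT-B analyses (SAP 8.5.2, 8.5.3) do not use the rule either.

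**Conclusion.** The point holds in limited form. As worded, the rule leaves unconfirmed a worsening that is on the last cycle form and still present at EoT, and it can never confirm one first recorded at EoT. Worsening is therefore probably under-counted, and possibly unequally if time on treatment differs by arm. Worsening on two consecutive cycle forms before stopping is captured.

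The number of patients affected cannot be derived from the documents. The percentages above assume that time on treatment equals PFS and is exponential. The plan gives no expected time on treatment for this trial, allows treatment past progression at the investigator's discretion (Protocol 3.3, 8.2.2), and allows earlier stopping for toxicity. The range from about 22% against 15% down to near 0% shows mainly how much turns on whether EoT counts and when patients stop.

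The consequence is small. This is one supplementary categorical analysis of an exploratory endpoint, tested at a nominal level without Type I error control (SAP 8.5). The primary and key secondary endpoints are untouched.

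**What to change.** In SAP 8.5.1:

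1. Define the confirming assessment as the next available one, including the EoT questionnaire, for improvement and worsening alike.
2. State that EoT scores count toward the two required change scores.
3. State the category given to an unconfirmed change.
4. Add a sensitivity analysis that treats a change on the last available form, in either direction, as met when no later form exists, and that includes patients with one post-baseline score.

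The cost is a few lines of SAP text and one extra derivation. No new data are needed, since the EoT form is already collected. The sensitivity analysis will admit some unconfirmed noise, which is why it should sit beside the main classification and not replace it. Any exclusion percentages quoted with it should carry their assumptions.
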